A sample of 28 subjects provides at least 80% power for testing our primary endpoint in a non-inferiority framework comparing the exercise-enabled MPC algorithm with missed meal insulin detection to use of participant's personal closed loop system. Assumptions informing this calculation were derived from simulations showing an expected mean percent time in range (70-180 mg/dL) for control IQ that was 3.7% lower (as a difference rather than a ratio) and standard deviations (SDs) for the two conditions of approximately 16 to 19. From this, we assume the SD of the within-subject difference will be approximately 17% and use a one-sided paired t test at the 0.025 level of significance for a mean difference of 3.7% time in range versus 6% as the non-inferiority margin. We plan to recruit up to 36 subjects with goal enrollment of 30 subjects (about 15 at each center).

Protocol Summary:

Participants will undergo one 7-day Intervention Period and one 7-day Control Period in randomized order. During the 7-day intervention study, participants will wear an Omnipod to deliver Fiasp insulin and a Dexcom G6 CGM. The CGM system will provide sensed glucose data every 5 minutes. Sensed glucose data will be wirelessly transmitted via Bluetooth Low Energy (BTLE) from the Dexcom G6 transmitter to the smartphone master controller every five minutes. The smartphone will wirelessly communicate via BTLE to an Omnipod through a Personal Diabetes Manager (Insulet Corp.). The closed-loop system will receive activity data through a Polar M600 watch worn by the participant. Participants will eat one meal in clinic and complete system training on Day 1 and then spend the rest of the 7 days at home. During the 7-day Control Period, the participant will continue their usual diabetes care regimen using a t:slim X2 pump with Control IQ enabled or the Omnipod 5 closed loop system.

Participant Criteria

Inclusion Criteria:

1. Diagnosis of type 1 diabetes mellitus for at least 1 year.
2. Age 18 years and older.
3. Current use of a t:slim X2 insulin pump with the use of Control IQ or the Omnipod 5 system with closed loop enabled with Dexcom G6 or G7 for at least 12 weeks.
4. Willingness to use Fiasp insulin during intervention study
5. Lives with another person age 18 or older who will sleep in the house at night and that can attend the training on using the system.

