17. Chronic usage of any immunosuppressive medication (such as cyclosporine, azathioprine, sirolimus, or tacrolimus).
18. Bleeding disorder, treatment with warfarin, or platelet count below 50,000.
19. Allergy to Fiasp insulin.
20. Current administration of oral or parenteral corticosteroids.
21. Any life-threatening disease, including malignant neoplasms and medical history of malignant neoplasms within the past 5 years prior to screening (except basal and squamous cell skin cancer).
22. Current use of beta blockers or non-dihydropyridine calcium channel blockers.
23. Current use of any medication intended to lower glucose other than insulin (ex. use of metformin or liraglutide) or SGLT-2 inhibitors (for diabetes or other indications, ex. use of empagliflozin or ertugliflozin).
24. Gastroparesis
25. Low carbohydrate diet at the time of screening defined as less than 50 grams of carbohydrate per day.
26. Any clinically significant disease or disorder which in the opinion of the Investigator may jeopardize the participant's safety or compliance with the protocol.

Participant Recruiting:

Participants will be recruited from 2 sites in the United States, one of which will be Oregon Health & Science University (OHSU). Non-English speaking participants will not be recruited since this protocol would require the use of medical devices and mobile software that do not

have non-English versions available. Up to 60 participants may be screened in this study. Goal enrollment is 30 participants across both sites with up to 6 replacements as needed to collect data from 28 participants. However, re-screening is allowed up to one time per individual, no sooner than 2 weeks and no longer than 3 months and after initial screen. It is anticipated that each site will enroll about 15 participants, but this may be adjusted if needed to complete enrollment in a timely fashion.

Withdrawal Criteria

The participant may withdraw at will at any time or at the discretion of the Investigator.

A participant must be withdrawn if the following applies:

- Severe Hypoglycemia during the treatment period (control or intervention period). Severe hypoglycemia is defined as any event that required the assistance of another person to administer carbohydrate, glucagon, or other resuscitative actions.

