- Diabetic ketoacidosis during the treatment period (control or intervention period). Diabetic ketoacidosis is classified as: symptoms such as polyuria, polydipsia, nausea, or vomiting, serum ketones >1.5 mmol/L or moderate/large urine ketones, either arterial blood pH<7.3 or venous pH<7.24 or serum bicarbonate <15, and treatment provided in a health care facility
- Other circumstances that would endanger the health of the participant if they were to continue participation in the study
- Protocol deviation having influence on efficacy or safety data as judged by the Investigator.
- Substantial and repeated non-compliance with trial procedures.
- Pregnancy.
- Intention of becoming pregnant.

Visit Procedures

Screening (Visit 1)

Screening will take place within 12 weeks prior to the first 7-day Visit. The participant will be sent the consent form prior to the screening by email so that they can have time to read it fully at their leisure and prepare any questions they might have. Upon arrival and prior to any procedures, study staff will explain the study, give the participant ample time to ask questions and consider participation, and ensure that the participant voices understanding of the informed consent and study requirements. To minimize the possibility of coercion and to ensure that participant is signing the appropriate version of the consent, an informed consent checklist will be used by study staff. After the participant has signed the consent, a copy of the consent/authorization form will be given to the participant. The original will be kept for the source document.

Study personnel will review medical history, and medications. Height, weight, pulse, and blood pressure will be obtained. A study investigator will perform a physical examination, excluding

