For the 7-Day Control Period, women of childbearing potential will receive a urine pregnancy test if the last pregnancy test was more than 7 days prior. This test must be negative before further participation is allowed. A capillary blood glucose (CBG) will be measured. Participants will complete a virtual visit by WebEx or Microsoft Teams or in person to start this visit. The purpose of this visit is to assist the participant with downloading: 1) the Dexcom Clarity app and sharing their data with the site, 2) the t:connect app and pairing it to their pump on their personal phone 3) Tidepool uploader app or 4) for Omnipod 5 users, logging in to their account at <https://insuletid.com/> from a computer/laptop/mobile browser and selecting to connect to

Glooko. If participants already have these apps on their phones, the visit will be used to confirm that data sharing is in place. The participants will continue to use their personal closed loop system, either the t:slim X2 pump with Control IQ or Omnipod 5, and their own insulin during the 7-Day Control Period. They will be instructed to take boluses prior to meals as they usually would. Participants will be asked to check their capillary blood glucose for symptoms of hypoglycemia or hyperglycemia if discrepant with CGM reading and in response to CGM alerts.

Participants will be given an instruction card (see Appendix C) for carbohydrate treatment before exercise to follow, if participants choose to exercise as part of their week. On the seventh day, participants will connect virtually by WebEx or Teams with study staff to share their pump download and confirm Dexcom Clarity data has been shared. A capillary blood glucose (CBG) will be measured. If the participant is not able to send the pump download and/or Clarity data is not being shared, the participant will come into clinic so that staff can download their devices.

7-Day Intervention Period

The participant will be asked to check his/her glucose before driving to the clinic and to bring a snack in the car in case hypoglycemia does occur (in which case, the participant must park and treat the hypoglycemia). For the 7-Day Intervention Period, women of childbearing potential will receive a urine pregnancy test if the last pregnancy test was more than 7 days prior. This test must be negative before further participation is allowed.

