Missing data: Our primary approach will include all available data as an intention-to-treat analysis, regardless of whether study subjects completed both arms. An observation will be included if at least 24 hours of data are available. However, we expect very low levels of missingness; in our previous four-arm crossover study, only one subject withdrew before completing at least two arms. Dropped CGM values will be interpolated over short time periods, using capillary values for calibration when available. In the event of $\geq 10\%$ missingness in either subject data or CGM values, we will analyze outcomes under multiple imputation to compensate for potential bias.

Additional considerations for selected secondary endpoints: The coefficient of variation of glucose is non-normal without an obvious probability distribution, so that bootstrapping will be

our primary approach for this endpoint. Data for percent of time with sensed glucose <54 mg/dl may be sparse; if so, we will present counts of events where glucose went below this level, counting as separate events when the time between them is ≥ 30 minutes.

Confidentiality and Protection of Human Participants

RISKS and BENEFITS

Risks: Given pumps and sensors used within automated glucose control systems are imperfect, there is a risk for hyperglycemia and hypoglycemia, which is mitigated by use of CGM alarms, protocols for managing hypoglycemia and hyperglycemia, and remote monitoring of the first 5 participants. A study investigator will be on call at all times.

Rarely, there can be allergic responses to insulin, such as skin redness, hives, itching of the skin, swelling of the mouth, or breathing difficulties. These reactions are considered very unlikely.

The following events have been identified as possible anticipated device-related adverse events of Dexcom G6 sensor insertion and wear:

- Excessive pain or discomfort from either system deployment or during wear period (8 or greater on a 10-point Likert scale)
- Excessive bleeding, defined as requires removal of the device to stop bleeding
- Hematoma, defined as induration at the sensor insertion location (ecchymosis is a known consequence of needle skin puncture or pressure from sensor pod and will not be captured as an AE)
- Edema from sensor and/or adhesive tape that is significant and non-resolving within 48 hours of sensor pod removal

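### Mandatory withdrawal for deviations judged to affect efficacy data, together with replacement and a paired main test, lets the compared pairs be selected by a judgement related to outcome

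*Protocol*

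**What the plan says.** Under Withdrawal Criteria the protocol first gives a general permission: "The participant may withdraw at will at any time or at the discretion of the Investigator". A mandatory list follows, introduced by "A participant must be withdrawn if the following applies". Beside severe hypoglycemia, ketoacidosis, endangerment and pregnancy, the list contains "Protocol deviation having influence on efficacy or safety data as judged by the Investigator" and "Substantial and repeated non-compliance with trial procedures". It does not define a deviation that counts as influential, and it gives no review of the decision by someone unaware of treatment.

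Participant Recruiting adds: "Goal enrollment is 30 participants across both sites with up to 6 replacements as needed to collect data from 28 participants". The Power Analysis gives the same ceiling: "We plan to recruit up to 36 subjects with goal enrollment of 30 subjects (about 15 at each center". Neither place says which losses may be replaced, or whether a replaced participant stays in the analysis.

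On analysis, Missing data states: "Our primary approach will include all available data as an intention-to-treat analysis, regardless of whether study subjects completed both arms". A period counts once it has 24 hours of data. Statistical methods names a paired Wilcoxon test as the main approach, concedes that it cannot handle missing data, and offers a linear regression with bootstrapped standard errors as a supplement.

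No blinding is described. The two conditions are visibly different systems. In the control week, "The participants will continue to use their personal closed loop system, either the t:slim X2 pump with Control IQ or Omnipod 5".

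**The concern.** One mandatory ground for ending participation refers to efficacy data and rests on the judgement of an investigator who knows which system is in use. A participant lost on that ground can be replaced. If the loss comes before both periods have usable data, the main test cannot use the participant, although the plan calls its primary approach intention-to-treat.

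In a non-inferiority comparison this matters more than usual. Suppose participants who manage the study system poorly are more likely to be judged to have an influential deviation. The pairs that remain then look better for that system than the randomised group would, and the final 28 pairs do not show it. The loss is also partly avoidable: the control period is usual care on the participant's own devices, and Visit Procedures allows it to start up to 8 weeks after the first period began.

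**Working it through.** **1. The plan's own figure.** Inputs from the Power Analysis: difference 3.7 points in favour of the study system, margin 6, SD of the paired difference 17, n = 28, one-sided 0.025.

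- Standard error = 17/√28 = 3.21.
- Noncentrality = (3.7 + 6)/3.21 = 3.02.
- Power from the noncentral t with 27 df = 82.9%, which agrees with the stated minimum of 80%.

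With the 7-point margin of the Study Hypothesis, power is 89.4%. The sample size is not in dispute here. The difference between 6 and 7 is a separate matter, so both margins are carried below.

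**2. Who drops out of the main test.** This follows from the mandatory withdrawal rule, the 24-hour rule and the paired test.

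- Withdrawn during the first period, either sequence: the second period is not run, so there is no pair.
- Withdrawn in the second period before 24 hours of data: no pair.
- Withdrawn in the second period after 24 hours: a pair exists and the main test uses it.

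A participant in one of the first two groups with 24 hours in one period enters only the supplemental regression. The model written there has terms for treatment, sequence and period and none for the subject, so a one-period participant contributes only a comparison between people.

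**3. How many.** The ceiling is 36 − 28 = 8 participants, or 8/36 = 22%. If the goal of 30 is met and 28 form pairs, it is 30 − 28 = 2, or 2/30 = 6.7%.

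**4. Possible size (illustration; the correlations are assumptions).** Paired differences d are normal with mean −6 (exactly at the 6-point margin) and SD 17. Each of 28 + k participants gets a score s = ρ(d + 6)/17 + √(1 − ρ²)·e, with e standard normal. The k lowest scores are lost. The other 28 are tested with the one-sided paired t test at 0.025 (20,000 runs). Bias is the mean of the retained differences minus −6.

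| ρ | k = 2: bias, type I error | k = 8: bias, type I error |
|---|---|---|
| 0 | 0, about 0.025 | 0, about 0.025 |
| 0.25 | +0.5, 0.035 | +1.6, 0.071 |
| 0.5 | +1.1, 0.057 | +3.2, 0.182 |
| 1 (always the worst results) | +2.2, 0.137 | +6.3, 0.68 |

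Cross-check: the bias should scale with ρ. For k = 2, 0.25 × 2.2 = 0.55 and 0.5 × 2.2 = 1.1. For k = 8, 0.25 × 6.3 = 1.6 and 0.5 × 6.3 = 3.15. These agree with the table to rounding and simulation error.

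Against the margin:

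- k = 2: 0.5/6 = 8% to 1.1/6 = 18% of 6 points, or 7% to 16% of 7.
- k = 8: 1.6/6 = 27% to 3.2/6 = 53% of 6 points, or 23% to 46% of 7.

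A paired Wilcoxon test run for the ρ = 1 row gave errors of 0.021 (k = 0), 0.103 (k = 2) and 0.59 (k = 8), so the pattern does not depend on using the t test.

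**The case against.** The other side has real substance.

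- **Safety content.** The deviation bullet covers safety data as well as efficacy data. Trial procedures include glucose and ketone checks and an overnight companion, so non-compliance can be a safety matter. This stands, and it limits the fix.
- **Data are kept.** Nothing says that withdrawal deletes data. The 24-hour rule and the supplemental model retain what was collected, and a prematurely stopped visit may be repeated. This stands, but a repeat is optional and the main test still needs both periods.
- **Imputation.** Multiple imputation is planned from 10% missingness. Counted by participant, it would be triggered at 22% but not at 6.7%. It makes up for outcome-related loss only as far as the imputation model captures the reason for the loss.
- **Rarity and direction.** The plan expects little missingness and reports one early withdrawal in its previous four-arm crossover study. Losses also arise from withdrawn consent, pregnancy or technical failure. Poor adherers may do badly in both weeks, and withdrawals during the control week could push the other way. This stands: neither the number nor the sign is known.
- **The SAP.** Analysis sets are often left to an SAP, which is not at hand. The withdrawal rule, the paired main test and the intention-to-treat statement are, however, all fixed in the protocol.

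A reader might infer more than this. One inference is that the investigator removes poor responders; in fact the rule requires a protocol deviation or substantial, repeated non-compliance, and a poor glucose result is neither. Another is that control-week data stay unseen until day 7; in fact 7-Day Control Period sets up or confirms Dexcom Clarity sharing with the site at the start. A third is that every intervention week is actively watched; in fact active remote monitoring is planned for the first 5 participants and can end if the safety criteria are met.

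**Conclusion.** The point holds as a possibility that the rules create. Mandatory withdrawal on an unblinded judgement about efficacy data, replacement of unspecified losses, and a main test that needs both periods do not fit the intention-to-treat statement. Together they allow the compared pairs to be selected by a judgement related to outcome, which may favour non-inferiority.

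The documents do not support the stronger statement that the compared set is in fact chosen by outcome, or that 22% will be lost in this way. Eight is the most that the enrolment limits allow, for all reasons combined. The size rests on assumed correlations, normal differences, an SD of 17, and every loss failing to form a pair. A correlation of the opposite sign would reverse the bias. That the investigator is unblinded is inferred from the design, since the protocol does not use the term for this trial.

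**What to change.** 1. In Withdrawal Criteria, remove influence on efficacy data as a ground for mandatory withdrawal and record such deviations instead. Leave the safety-related grounds and the investigator's discretion as they are.
2. State that stopping the study system, including for non-compliance, does not by itself end data collection. Where consent remains and the investigator has no safety objection, keep the intervention CGM data already obtained and still collect the usual-care control period from downloads of the participant's own devices.
3. State that a replaced participant stays in the analysis. All randomised participants with 24 hours or more of data in any period should enter the primary analysis by a method that accepts one-period data, such as a mixed model with a subject effect, treatment and period. Keep the paired Wilcoxon test as a supporting analysis.

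Step 2 matters most for bias, because a mixed model corrects for loss only as far as the observed data explain it. The cost is amended wording and downloads that the site already takes. The downside is that some low-adherence weeks stay in the primary result, so the estimate may be slightly less favourable to the study system.

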At the completion of the 6-hour in-clinic visit, participants will be discharged from the clinic. Capillary blood glucose will be measured prior to discharge. Participants will wait to discharge home if capillary blood glucose is <85 and or >300 mg/dl or at the discretion of the study investigator, and treatment will be at the discretion of the study investigator. Once participant's capillary blood glucose is between 85-300 mg/dl on two capillary blood glucose measurements completed at least 30 minutes apart, they can be discharged home. If the capillary glucose is less than 85mg/dL, participants will be asked to consume 15g of glucose tablets. They can then be discharged if the next capillary glucose measurement 30 minutes later is greater than 85mg/dL. If the capillary blood glucose is <70 , participants will be asked to consume 15g of glucose tablets and recheck capillary blood glucose every 15 minutes until >70 . If capillary blood glucose is greater than 300mg/dL, participants will be instructed to pause iPancreas closed loop mode, take a correction bolus from the bolus calculator after reviewing this dose with the study investigator who will modify dose if needed considering current insulin on board then resume iPancreas closed loop mode. The participant can then be discharged home if the next capillary blood glucose measurement 30 minutes later is less than 300 mg/dL or if the CGM glucose trend arrow shows flat arrow (Increasing/decreasing less than 1 mg/dL each minute) or a down arrow (decreasing >30 mg/dL in 30 minutes). Participants will be instructed to eat meals and snacks as they normally would at home. Participants will be instructed that his/her companion will be required to stay with them each night while an outpatient.

Return to the Outpatient Clinic

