On the seventh day, participants will return to the outpatient clinic. The study will be terminated and the participant's own insulin pump will be restarted. The study investigator will consult with the participant regarding appropriate insulin dosing for the remainder of the day. The Polar watch, Omnipod and Dexcom sensor will be removed from the participant. All infusion and sensor sites will be inspected for signs of irritation or infection. In addition, the sensor will be inspected for the possibility of breakage or fracture. If there is any evidence of sensor breakage, it will be recorded. If an area of inflammation of 1 cm or greater exists around the point of insertion, a de-identified photograph will be taken of the area and the participant will return 1-3 days later for a follow-up visit. A capillary blood glucose value will be taken immediately prior to discharging the participant. Participants will be given oral carbohydrate for values below 85 mg/dl, and if capillary blood glucose is greater than 180mg/dL, participants will be instructed to take a correction bolus from their home insulin pump per their usual home settings after reviewing this dose with the study investigator who will modify dose if needed considering current insulin on board. The participant can then be discharged home if the next capillary blood glucose measurement 30 minutes later is less than 300 mg/dL or if the CGM glucose trend arrow shows flat arrow (increasing/decreasing less than 1 mg/dL each minute) or a down arrow (decreasing >30 mg/dL in 30 minutes).

There is the option to complete this visit by WebEx or Microsoft Teams. Participants will be given shipping boxes for sending all devices back. Participants will connect with a study coordinator and investigator virtually to complete the visit.

If a study visit is stopped prematurely, such as due to technical problems, the participant will be asked if they can repeat the study visit that was terminated early with additional compensation provided. Repeating the study visit will be optional.

Hypoglycemia Treatment Guidelines

CBG < 70 mg/dl

- Give 15 grams of oral carbohydrate.
- Repeat treatment every 15 minutes as needed to raise blood glucose ≥ 70 mg/dl.

Presence of STUPOR, LOSS OF CONSCIOUSNESS, or SEIZURE

- Administer rescue glucagon per the manufacturer's instructions.
- Verify that insulin is turned off.
- Further management per study investigator.

Hyperglycemia Treatment Guidelines

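### For participants treated for a reading below 85 mg/dL, the Day 7 discharge text is inconsistent with Day 1: it states no recheck result on the low side that releases them

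*Protocol*

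**What the plan says.** **Day 7, Return to the Outpatient Clinic.** The study devices are removed, the participant's own pump is restarted, and a fingerstick is taken just before discharge. The treatment sentence reads "Participants will be given oral carbohydrate for values below 85 mg/dl, and if capillary blood glucose is greater than 180mg/dL", and the second group takes a correction bolus from the home pump after the investigator has reviewed the dose. One release sentence follows: "The participant can then be discharged home if the next capillary blood glucose measurement 30 minutes later is less than 300 mg/dL". A flat or down sensor arrow is an alternative, defined as "increasing/decreasing less than 1 mg/dL each minute) or a down arrow (decreasing >30 mg/dL in 30 minutes".

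**Day 1, Discharge from inpatient clinic.** There are three relevant statements:
- The general rule: "Once participant's capillary blood glucose is between 85-300 mg/dl on two capillary blood glucose measurements completed at least 30 minutes apart, they can be discharged".
- For participants below 85 mg/dL who have taken glucose tablets: "They can then be discharged if the next capillary glucose measurement 30 minutes later is greater than 85mg/dL".
- For participants above 300 mg/dL who have taken a correction bolus: "The participant can then be discharged home if the next capillary blood glucose measurement 30 minutes later is less than 300 mg/dL or if" the arrow is flat or down.

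**Hypoglycemia Treatment Guidelines.** These apply below 70 mg/dL: "Repeat treatment every 15 minutes as needed to raise blood glucose ≥ 70 mg/dl". They do not mention discharge.

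**The concern.** Both visits start carbohydrate at the same value, 85 mg/dL. Only Day 1 says what result lets a treated participant leave. The single Day 7 release sentence looks only upward: it sets a ceiling and accepts a falling arrow, and it has no floor.

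This is a matter of participant safety, not of analysis. The sentence applies when one insulin delivery system has just been stopped and another restarted. The protocol itself asks the investigator to weigh insulin still active when reviewing a correction dose at that point. It also treats a low while travelling as a recognised risk: the 7-Day Intervention Period section has participants check glucose before driving to the clinic and carry a snack. Staff who follow the Day 7 text literally could release a participant with a low or falling value, or could find no instruction for that participant at all.

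**Working it through.** The protocol gives no figure to reproduce here, and no sample size, power or error rate depends on the point. The check applies each release sentence literally and compares the results.

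**Rules as written**
- Day 7 release sentence: recheck < 300, or arrow flat or down.
- Day 1 general rule: two readings from 85 to 300, at least 30 minutes apart.
- Day 1 branch for a first reading < 85: recheck > 85.
- Day 1 branch for a first reading > 300: recheck < 300, or arrow flat or down.

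**Illustrative cases** (chosen to exercise the rules, not taken from data; the Day 7 column assumes that the sentence covers every treated participant)

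| First reading → recheck (mg/dL), arrow | Day 7 release sentence | Day 1 branch | Day 1 general rule |
|---|---|---|---|
| 80 → 75, flat | met | low branch: not met | not met |
| 80 → 60, down | met | low branch: not met | not met |
| 200 → 65, down | met | none at 200 | not met |
| 320 → 65, down | met | post-correction branch: met | not met |
| 320 → 310, down | met | post-correction branch: met | not met |

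**Low group (rows 1 and 2).** The word *then* in the Day 7 sentence can be read in two ways.
1. It refers to both treated groups. A participant treated at 80 who rechecks at 75, or at 60 and falling, meets the Day 7 sentence and fails Day 1.
2. It refers only to the bolus group. A participant treated at 70-84 then has no stated recheck and no stated release result. Below 70 the treatment guideline repeats carbohydrate until 70 is reached, but it is not a discharge rule and does not act at 70-84.

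The two readings exclude each other. Neither gives the low group the recheck criterion that Day 1 gives it.

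**Correction group (rows 3 to 5).** Above 300 the release test is the same on both days, and neither has a lower limit. A fall from 320 to 65 passes both. What it fails is the general 85-300 rule in the Day 1 section, so the conflict lies inside that section. At 200, Day 1 has no correction branch to compare with. Its general rule would not be met by a recheck of 65, whereas the Day 7 sentence would be.

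**The case against.** The strongest reply is that the release sentence comes directly after the bolus clause and nearly repeats the Day 1 sentence for readings above 300. A ceiling of 300 and a reassuring down arrow make sense only after a high, so few readers would apply them to someone just given carbohydrate. That is fair, and the narrow reading is the more natural one. It does not help the low group, which then has no release criterion.

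Safeguards do exist. The fingerstick is taken immediately before discharge, so a new value below 85 would arguably prompt carbohydrate again. The guideline covers readings below 70. The investigator advises on dosing for the rest of the day, and the release wording permits discharge without requiring it. These narrow the gap mainly to 70-84 mg/dL. They do not state a release result, and the Day 7 section has no counterpart to the explicit Day 1 provision that the investigator may hold a participant.

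The visits also differ. Day 1 sends a participant home on an investigational system, while Day 7 returns the participant to a system used for at least 12 weeks before entry. Different rules could be intended, so the two texts are better called inconsistent than contradictory. The protocol gives no reason for the difference.

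A reader might infer that Day 7 also contradicts Day 1 for a participant who falls after a correction bolus. The documents do not support that, because the Day 1 branch above 300 uses the same test without a floor. A reader might also infer that every participant is exposed. Only those reading below 85 or above 180 reach the disputed text, and the visit may be held by video, so some participants may have no clinic discharge.

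**Conclusion.** The point holds for participants treated for a reading below 85 mg/dL on Day 7. Depending on how the release sentence is read, either someone still low or falling meets it, or those treated at 70-84 have no stated recheck or release criterion. It would be wrong to charge the plan with both faults at once.

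The missing lower limit after a correction bolus is a separate wording problem. It is present at both visits, and on Day 1 it conflicts with that section's own general rule.

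The size cannot be calculated. Goal enrolment is 30, with up to 36 recruited, but only participants below 85 or above 180 at the Day 7 check are affected, and the protocol gives no basis for estimating how many that is. The conclusion rests on the literal wording and assumes that no separate site instruction supplies the missing criterion. The primary endpoint, the power and the analysis are unaffected.

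**What to change.** Reconcile the sections Discharge from inpatient clinic and Return to the Outpatient Clinic. In the Day 7 text, state separately:
- for participants treated for a low reading, which recheck result releases them;
- for participants given a correction bolus, which recheck result releases them;
- whether the test of under 300 mg/dL, or a flat or down arrow, applies to the low group at all.

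In the Day 1 text, say how the release test after a correction bolus relates to the general 85-300 sentence. If the two visits are meant to differ, a short reason would settle the matter. The clinical team sets all values; none is proposed here.

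The cost is a wording change to the protocol and, at most, one more fingerstick for a few participants.
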